3.1.1. Futility analyses

At least one interim analysis for futility will be performed. The first analysis will occur at Interim Analysis 2, i.e. when 300 participants complete 84 days of treatment, or when approximately 400 participants remain to be randomized, whichever occurs first.

Futility will be assessed in a sequential manner.

- 1) Futility will first be assessed for the primary endpoint of change from baseline in FEV₁ at Day 84 by fitting a suitable dose response model, as described in Section 7.1.2.
- 2) If the posterior predictive probability of declaring success for this endpoint is low across all doses, then futility will be assessed for the rate of (on-treatment) exacerbations endpoint.
- 3) If the posterior predictive probability of declaring success for this endpoint is low, then the study may be stopped.

Any decision to stop will be made after a review of all the data summarised/analysed at the time of the interim, including the proportion of participants achieving the EXACT-defined recovery.

3.1.1.1. Futility rules

The decision rules for futility are defined as follows.

Change from baseline in FEV₁ at Day 84

Stop study for futility if the predictive probability of success at the end of the trial, given the data at the interim is <20%, across all doses, where success at the end of the trial for change from baseline in FEV₁ is defined as demonstrating >90% posterior probability that the true difference from placebo for any dose of nemiralisib is greater than 0.

Rate of on-treatment (moderate/severe) exacerbations

Stop study for futility if the predictive probability of success at the end of the trial, given the data at the interim is <20%, where success at the end of the trial for rate of exacerbations is defined as demonstrating >80% posterior probability that the true rate reduction on 750 mcg dose versus placebo > 0%.

If a different dose arm appears to be more efficacious than the 750 mcg arm, then futility may be assessed using the rate reduction for this arm versus placebo.

The pre-determined rules will act as guidelines for stopping the study for futility. All of the data summarised/analysed at the time of the interim will be reviewed prior to any decision to stop the study.

3.2. Final Analyses

The final planned primary analyses will be performed after the completion of the following sequential steps:

1. All participants have completed the study as defined in the protocol.
2. All required database cleaning activities have been completed and final database release (DBR) and database freeze (DBF) has been declared by Data Management.
3. All criteria for unblinding the randomization codes have been met.
4. Randomization codes have been distributed according to RandAll NG procedures.

4. ANALYSIS POPULATIONS

Population	Definition / Criteria	Analyses Evaluated
All Participants Enrolled (APE) Population	
 All participants who are screened for eligibility. 	
 Study Population
Modified Intent To treat (MITT) Population	
 All randomized participants who receive at least one dose of study treatment. Participants will be analyzed according to the treatment that they were randomized to. 	
 Study Population Efficacy
Per Protocol (PP) Population	
 All randomized participants who receive at least one dose of study treatment, excluding any participants with an important protocol deviation. Participants will be analyzed according to the treatment that they were randomized to. 	
 Sensitivity analyses of efficacy
Safety Population	
 All randomized participants who received at least one dose of study treatment. Participants will be summarised according to the treatment that they actually received. 
 If participants receive >1 treatment, then they will be summarised according to the most frequently dosed treatment. In cases where the frequency is equal, the participant will be assigned the lowest dose strength of nemiralisib 	
 Safety
Pharmacokinetic (PK) Population	
 All participants in the Safety population who had at least 1 non-missing PK assessment (Non-quantifiable [NQ] values will be considered as non-missing values). Participants will be summarised according to the treatment that they actually received 	
 PK

Refer to [Appendix 11](#): List of Data Displays which details the population used for each display.

4.1. Protocol Deviations

Important protocol deviations (including deviations related to study inclusion/exclusion criteria, conduct of the trial, patient management or patient assessment) will be summarised and listed.

Important deviations which result in exclusion from the analysis population will also be summarised and listed. (Please refer to [Appendix 1](#): Protocol Deviation Management and Definitions for Per Protocol Population).

Protocol deviations will be tracked by the study team throughout the conduct of the study in accordance with the Protocol Deviation Management Plan.

- Data will be reviewed prior to unblinding and freezing the database to ensure all important deviations and deviations which may lead to exclusion from the analysis are captured and categorised on the protocol deviations dataset.
- This dataset will be the basis for the summaries and listings of protocol deviations.

A separate summary and listing of all inclusion/exclusion criteria deviations will also be provided. This summary will be based on data as recorded on the inclusion/exclusion page of the eCRF.

5. CONSIDERATIONS FOR DATA ANALYSES AND DATA HANDLING CONVENTIONS

5.1. Study Treatment & Sub-group Display Descriptors

Treatment Group Descriptions			
RandAll NG Randomization System		Data Displays for Reporting	
Code	Description	Description	Order in TLF
A	Placebo	Placebo	1
B	GSK2269557 12.5 mcg	NEMI 12.5 mcg	2
C	GSK2269557 25 mcg*	NEMI 25 mcg	3
D	GSK2269557 50 mcg	NEMI 50 mcg	4
E	GSK2269557 100 mcg	NEMI 100 mcg	5
F	GSK2269557 250 mcg	NEMI 250 mcg	6
G	GSK2269557 500 mcg	NEMI 500 mcg	7
H	GSK2269557 750 mcg	NEMI 750 mcg	8

* The nemiralisib dose of 25 mcg may be added following the results of an un-blinded interim analysis if further characterization of the lower end of the dose response curve is required.

Treatment comparisons will be displayed as follows using the descriptors as specified:

1. NEMI 12.5 mcg vs Placebo
2. NEMI 25 mcg vs Placebo
3. NEMI 50 mcg vs Placebo
4. NEMI 100 mcg vs Placebo
5. NEMI 250 mcg vs Placebo
6. NEMI 500 mcg vs Placebo
7. NEMI 750 mcg vs Placebo

5.2. Baseline Definitions

For all endpoints, the baseline value will be the latest pre-dose assessment with a non-missing value, including those from unscheduled visits. If time is not collected, Day 1 assessments are assumed to be taken prior to first dose and used as baseline.

Post-bronchodilator Baseline FEV₁ is defined as the latest FEV₁ measured prior to the first dose of study treatment and post-bronchodilator.

Pre-bronchodilator Baseline FEV₁ is defined as the latest FEV₁ measured prior to the first dose of study treatment and pre-bronchodilator.

Baseline CAT Total Score is defined as CAT Total Score measured prior to the first dose of study treatment on Day 1.

Baseline SGRQ Total Score is defined as SGRQ Total Score measured prior to the first dose of study treatment on Day 1.

Unless otherwise stated, if baseline data is missing no derivation will be performed and baseline will be set to missing.

A centred baseline will be derived for each participant by subtracting the mean baseline across all participants from each participant's baseline value. The 'centred' baseline may be used instead of Baseline in the statistical analyses to aid convergence.

5.3. Multicentre Studies

In this multicentre global study, enrolment will be presented by investigative site and country.

5.4. Examination of Covariates and Subgroups

5.4.1. Covariates

The list of covariates may be used in descriptive summaries and statistical analyses, some of which may also be used for subgroup analyses. The key covariates of interest are Index exacerbation severity, Smoking history and Region. Additional covariates of clinical interest may also be considered. The decision to include covariates in the model will be based on their impact on the model fit and/or convergence and will be detailed in the CSR.

A centred covariate will be derived for each participant by subtracting the mean covariate across all participants from each participant's covariate value. The 'centred' covariate may be used in place of the covariate in the statistical analyses to aid convergence.

Covariate	Details
Index exacerbation severity	Categorical variable (Moderate or Severe) derived using the stratification variable from the randomisation system.
Age (at screening)	Continuous variable derived as described in Section 13.6.2.1
BMI	Continuous variable derived using Height and Weight variables collected in eCRF: BMI = Weight (kg) / (Height (m)) ²
Gender	Categorical variable (Male or Female), collected in eCRF
Country	Categorical variable
Region	Categorical variable derived using Country as: 
 • Americas: Canada, Mexico, United States • Asia: Australia, Korea • Eastern Europe: Poland, Romania, Russia • Western Europe: France, Germany, Italy, Netherlands, Spain, Sweden, U.K.
Smoking history	Categorical variable (Current or Former), collected in eCRF
Baseline COPD maintenance therapy type	Categorical variable derived depending on data observed. Possible categories of interest are: Monotherapy vs. Dual therapy vs. Triple therapy
Index exacerbation type	Categorical variable: New or Relapse, derived using the question: "Other than the current prescription, for the index exacerbation, has the subject received oral/systemic corticosteroids and/or antibiotics for a COPD exacerbation within the last 7 days?" in the eCRF: New = No Relapse = Yes
Number of exacerbations in the previous 12 months	Categorical variable derived from "Total number of COPD exacerbations in the last 12 months" in the eCRF. Possible categories of interest are: 0 vs. 1 vs. ≥2
Baseline COPD ICS therapy use	Categorical variable (ICS Use or Non-ICS Use) derived from review of concomitant medications
Baseline Blood Biomarker Status	Categorical variable derived from Screening time-point for the following: 
High sensitivity CRP
 
 • Bacterial: >10 mg/L • Non-Bacterial: ≤10 mg/L 
Procalcitonin
 
 • Bacterial: >0.1 µg/L • Non-Bacterial: ≤ 0.1 µg/L 
Eosinophils
 
 • High: ≥0.15 GI/L • Low: <0.15 GI/L

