2.2. Study Design

This is a Phase IIb, multicenter, randomized, stratified (by index COPD exacerbation severity [moderate or severe] and by whether or not the participant is in the PK Subgroup), double-blind (Sponsor Open), placebo-controlled, parallel-group study in participants who present with an acute moderate or severe exacerbation of COPD requiring Standard of Care (SoC).

This study consists of a Screening Period, a 12-Week Treatment Period and a 12-Week Post-Treatment Follow-Up Period. Randomization and the first dose of the double-blind study treatment administration (Visit 2/Day 1) should take place in the morning, as soon as possible following determination of eligibility and completion of the baseline measures, including the EXACT-PRO questionnaire for the day of randomization, and FEV₁ measurement and no later than 48 hours after the start of SoC.

PK Subgroup: Sparse PK sampling will be conducted in a subgroup of participants at selected sites. The PK Subgroup will be identical to the main study in terms of the study population, design, and conduct, with the exception of blood draws (3 per visit on Days 14 and 28) for PK analysis.

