7.1.2. Primary Statistical Analyses

The primary endpoint will be analysed by fitting a suitable dose response model. The following models will be fitted, and the one that gives the best fit to the data will be selected: Bayesian 4-parameter E_{max} dose response model, 3-parameter E_{max} model and a Log-linear model.

The 4-parameter E_{max} dose response model will take the form:

$$\text{Change from baseline FEV}_1 = (E0 + a_1 * \text{baseline}) + \frac{(E_{\max} + b_1 * \text{baseline}) * \text{Dose}^\gamma}{ED50^\gamma + \text{Dose}^\gamma}$$

The 3-parameter E_{max} dose response model will take the form:

$$\text{Change from baseline FEV}_1 = (E0 + a_1 * \text{baseline}) + \frac{(E_{\max} + b_1 * \text{baseline}) * \text{Dose}}{ED50 + \text{Dose}}$$

Where: E0 = the response at dose = 0 (placebo)

E_{max} = the maximal response

ED50 = the dose that yields 50% of the maximal response

γ = the slope parameter

a₁, b₁, are covariates for explanatory parameters

Initially, normal non-informative priors will be used for the E0, a₁, a₂, and E_{max} parameters with mean 0 and standard deviation 1E6 L. A functional uniform prior will be used for the ED50 and slope parameters ([Bornkamp, 2014](#)), where the prior density for the functional uniform prior is based on all the parameters in the model. An inverse -

gamma prior with shape of 0.001 and scale of 0.001 will be used for the residual variance. However, if a prior distribution appears not to be truly non-informative then alternative prior distributions may be used.

Parameters will be blocked such that the MCMC procedure samples from E_0 , a_1 , b_1 , and E_{\max} , first, then the ED50 and slope parameters and then finally the residual variance parameter. For the functional uniform priors, the density will be calculated for values of dose from 0.0001 to 750 in steps of 50 (i.e. 0.0001, 50.0001, 100.0001, ..., 750.0001). For the continuous covariates, the density will be calculated from the minimum to the maximum in 10 equal steps. For binary covariates the density will be calculated for values 0 and 1. If the model does not converge including covariates, the model may be fitted with covariates removed.

If the log-linear model is fitted an offset of 1 will be used.

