7.1.3. Sensitivity and Supportive Analyses

If there are greater than 20% of participants with an important protocol deviation that results in exclusion from the Per Protocol Population, the primary analysis may be repeated using the Per Protocol Population.

Change from baseline in clinic visit trough FEV₁ at Day 84 will also be compared between treatment groups using a Bayesian Repeated Measures analysis with covariates for baseline-by-Day interaction and treatment-by-Day interaction. Day will be fitted as a repeated effect within each participant. All post-baseline scheduled visits will be included in the analysis using Day. Non-informative priors will be used for all modelling parameters. Wherever possible conjugate priors will be utilised. An unstructured covariance matrix will be used to model the within-subject error.

A further sensitivity analysis may be performed where Baseline FEV₁ is replaced with the FEV₁ measured post-bronchodilator and prior to dosing on day of hospital discharge for participants who were hospitalised for their index exacerbation, i.e. who were randomized with a Severe index exacerbation but kept as Baseline FEV₁ for participants who were randomized with a Moderate index exacerbation.

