7.2.1.1. Statistical analyses

The rate of exacerbations will be analysed using a Bayesian generalized linear model assuming a negative binomial distribution for the underlying exacerbation rate with a log link function. An offset to account for the length of time on treatment or in study, depending on the specified time-period, for each participant (as described above) will be included in the model as \log_e (length of time).

Non-informative priors will be used for all modelling parameters. Wherever possible conjugate priors will be utilised.

The median exacerbation rates for each dose arm per 12 weeks, along with the median ratio in exacerbation rates (nemiralisib/placebo) per 12 weeks for each dose, will be estimated and corresponding 95% HPD credible intervals presented. The probability that the true exacerbation rate ratio is less than 1, in addition to other values appropriately selected based on the data, will be presented.

Based on pharmacological predictions, the 500 mcg and 750 mcg doses are expected to result in similar levels of target inhibition and thus potentially translate to similar clinical benefit, therefore estimates of the exacerbation rates for pooled data from 500 mcg plus 750 mcg will also be presented.

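### Index exacerbation severity stratifies the randomisation but is committed to no main efficacy model; an undefined fit or convergence rule decides whether it enters

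*SAP*

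**What the plan says.** References are to the current SAP, the first of the versions in the file.

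- **Design.** Section 2.2 describes the trial as "stratified (by index COPD exacerbation severity [moderate or severe] and by whether or not the participant is in the PK Subgroup".
- **Covariate rule.** Section 5.4.1 states: "The key covariates of interest are Index exacerbation severity, Smoking history and Region". It commits none of them: "The decision to include covariates in the model will be based on their impact on the model fit and/or convergence". Its table lists 14 candidates, counting the three blood biomarkers separately, and the list is open: "Additional covariates of clinical interest may also be considered". The choice is to be reported in the study report.
- **Primary model.** The Emax equations in Section 7.1.2 carry baseline FEV1 only. Further covariates are foreseen but not named: "For binary covariates the density will be calculated for values 0 and 1". They can also be removed: "If the model does not converge including covariates, the model may be fitted with covariates removed".
- **Repeated measures.** Section 7.1.3 plans a "Bayesian Repeated Measures analysis with covariates for baseline-by-Day interaction and treatment-by-Day interaction".
- **Other main models.** For exacerbations, Section 7.2.1.1 says: "The rate of exacerbations will be analysed using a Bayesian generalized linear model assuming a negative binomial distribution". It adds an offset for time but names no covariate. The Cox model (7.2.2.1) and the logistic model (7.2.5.4) name none either.
- **Where severity is committed.** Only in subgroup analyses: Sections 7.1.4, 7.2.1.2, 7.2.2.2, 7.2.5.5 and 7.2.6.4.

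**The concern.** A stratification factor is normally fixed in the main models. It was chosen because it was thought prognostic, and the randomisation balances it. A linear or count model that omits it leaves the between-stratum variation in the residual, so the reported interval is wider than the design warrants.

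Here inclusion turns on a rule that two analysts could apply differently. No fit criterion, order of entry or time of decision is given. The SAP does not state when covariates are chosen, but the trial is sponsor-open (2.2), Clinical Statistics is unblinded at the interims (3.1), and the final analysis follows release of the randomisation codes (3.2). Since no blinded selection step is described, a choice made with treatment codes known is a fair inference.

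The choice also reaches interim decisions. The futility calculation in Section 7.1.2 takes the mean difference from placebo and its standard deviation from the fitted model, and Section 3.1.1.1 compares the result with a 20% guideline.

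**Working it through.** The SAP gives no SD, power, allocation ratio or prognostic effect of severity, so there is no planned figure to reproduce. What follows is illustration under stated assumptions.

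**1. FEV1 (linear model)**

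The severe share p = 50/170 = 0.294 is the planned mix at Interim Analysis 1 (3.1), assumed for the whole trial. Let d be the severity difference in residual SDs after baseline (assumed). Omitting severity multiplies the reported variance of a treatment difference by 1 + p(1−p)d², with p(1−p) = 0.208.

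| d | Variance factor | SE factor |
|---|---|---|
| 0.3 | 1.019 | 1.009 |
| 0.5 | 1.052 | 1.026 |
| 1.0 | 1.208 | 1.099 |

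For power, take the 90% posterior-probability success rule as about a one-sided 0.10 test and assume 80% power with severity fixed (1.282 + 0.842 = 2.123). Stratification keeps the arms balanced, so the estimate itself is no noisier; only the reported SE grows. Power without severity is Φ(2.123 − 1.282 × SE factor): 79.7%, 79.1% and 76.3% at d = 0.3, 0.5 and 1. If the estimate's own variance grew as well, as without balance, Φ(2.123/SE factor − 1.282) gives 79.4%, 78.5% and 74.2%, a lower bound for power.

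**2. Exacerbation rate (negative binomial)**

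Assumed: 30% severe, rates 0.70 (severe) and 0.35 (moderate) per 12 weeks, dispersion 0.8.

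- Mean rate: 0.7 × 0.35 + 0.3 × 0.70 = 0.455.
- Squared coefficient of variation between strata: 0.3 × 0.7 × 0.35² / 0.455² = 0.124.
- Without severity: dispersion becomes 0.8 × 1.124 + 0.124 = 1.02, and the per-patient variance of the log rate is 1/0.455 + 1.02 = 3.22.
- With severity: 1/[0.7 × 0.35/1.28 + 0.3 × 0.70/1.56] = 3.07.
- Ratio: 3.07/3.22 = 0.95, about 5% less variance, or about 2.4% in interval width.

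**3. Selecting severity instead of fixing it**

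The simulation used 4,000 runs per setting, two arms of 100 (assumed) and stratification on severity. It compared no covariate, severity fixed, the best AIC among the 8 subsets of the three key covariates, and the most favourable of the 8. AIC is a stand-in, because the SAP names no fit criterion for covariates.

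- Mean SE: 0.141 with severity fixed and 0.141 under AIC at every d. With no covariate it was 0.1425 at d = 0.3, 0.145 at 0.5 and 0.155 at 1.
- AIC kept severity in about 69% of runs at d = 0.3, 96% at 0.5 and 100% at 1.
- Null success rate: 0.089–0.105 with severity fixed, 0.091–0.104 under AIC, and 0.102–0.121 for the most favourable model. The Monte Carlo SE is about 0.005.
- Power with no covariate against severity fixed: 79.2% v 79.6%, 78.4% v 79.4% and 75.6% v 79.0% at d = 0.3, 0.5 and 1, in line with step 1.

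**4. Logistic and Cox models**

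No interval-width figure applies. Adding a prognostic covariate moves the target from a marginal to a conditional odds or hazard ratio. It generally does not narrow the interval on the log scale; the gain is in power.

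**The case against.** The strongest reply is that the SAP does not leave severity out. It is named first among the key covariates, is taken from the randomisation system, and binary covariates are provided for in the primary model. Section 5.4.1 is not limited to FEV1, so silence in the later sections does not exclude severity. A mechanical fit rule would usually keep it when it matters, at no cost in SE (step 3). Severity-specific results are planned in any case, and this is a Phase IIb dose-characterisation trial.

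Most of that stands, and it rules out three stronger readings.

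- **Precision is lost on every efficacy endpoint.** Not supported. Loss needs severity to be prognostic and also left out, most plausibly through the convergence clause. For odds and hazard ratios, interval width is not what is at stake.
- **The treatment effect guides the model.** Not supported. Fit and convergence are not the treatment effect, and an AIC rule left the null success rate unchanged. Even a free pick of the most favourable of 8 models added only 1 to 2 points, though a longer list and more endpoints could add more.
- **The SAP says covariates are chosen after unblinding.** It does not; that is an inference from Sections 2.2, 3.1 and 3.2.

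The reply does not supply a rule. The reassuring simulation rests on a mechanical criterion that the SAP does not set, and the convergence clause lets severity be the first covariate removed. The second stratification factor, PK subgroup, is also in no model. Section 2.2 describes that subgroup as the same as the main study apart from blood draws, so leaving it out should cost little.

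**Conclusion.** The point holds as a modest one. Severity is not committed to any main efficacy model, and the rule that decides on it has no criterion, order or blinded timing. The ambiguity is certain; the loss is conditional on severity being prognostic and left out.

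In that case the loss is about 5% of the reported variance of the log exacerbation rate, at a single set of assumed rates and dispersion. For FEV1, the SE is inflated by about 1–3% at 0.3–0.5 residual SD and by up to 10% at 1 SD, on an assumed severe share of 29%. In the logistic and Cox analyses the cost is power, and the estimand (conditional or marginal) depends on a data-driven choice. None of the prognostic effects comes from the SAP.

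**What to change.** In Section 5.4.1, replace the inclusion rule with a statement that index exacerbation severity, as recorded by the randomisation system, is a fixed covariate in all main efficacy models:

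- a shift in E0 in the dose-response models;
- severity-by-Day in the repeated-measures models;
- a main effect in the negative binomial, Cox and logistic models.

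Fix any other covariates before unblinding, or confine them to one pre-named sensitivity analysis. In Section 7.1.2, replace the open convergence clause with an ordered fallback that removes other covariates first and severity last, and report the model without severity. One sentence can say that PK subgroup is deliberately left out. Section 7.1.2 already lists a prior for a coefficient a2 that appears in no printed equation; the severity shift could use it.

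The cost is SAP wording and a term already in the data. The downside is one more parameter in the Emax model, with a small added convergence risk that the fallback covers.
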